7 STATISTICAL / ANALYTICAL ISSUES

7.1 General Rules

All statistical computations will be performed and data summaries will be created using SAS 9.4 or higher. If additional statistical packages are required, these will be discussed in the study report. For summaries of study data, categorical measures will be summarized in tables listing the frequency and the percentage of participants; continuous data will be summarized by presenting mean, standard deviation, median and range; and ordinal data will be summarized by only presenting median and range. Model-based analyses described in Section 9 will be used to obtain point estimates and associated confidence intervals for various measures as well as p-values for comparisons of data between treatment groups. Note: initial models will include the high dose treatment arm; however, if the model cannot converge due to the small number of participants randomized to this arm prior to removal from the study, then the model will only compare outcomes between the low dose and placebo treatments. P-values presented will be based on two-sided tests unless otherwise specified and generally only adjusted for randomization factors (study site, gender, and presence of concomitant antidepressants). Note: in the event a model cannot converge due to small sample sizes for a specific randomization factor, it will be removed from the model. For continuous outcomes, checks of normality will be performed and if required, transformations or non-parametric tests will be employed.

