7.6 Multicenter Studies

This is a 3-center study including Tuscaloosa Research & Education Advancement Corporation (TREAC)/Tuscaloosa VA Medical Center (TVAMC), Connecticut Research & Education Foundation (CREEF)/VA Connecticut Healthcare System (VACT), and Wayne State University. Although we initially expected the total number of enrolled participants to be roughly equal across the three study sites, only one participant from the Wayne State site enrolled and completed the study. Since randomization was stratified based on study site, site will be included as a term in all model-based analyses. Since only one participant was enrolled at Wayne State, this participant will be removed during sensitivity analyses so comparisons can be made between study site.

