9.3 Primary Efficacy Analysis Methods

The primary outcome for this study is a binary measure assessed at weeks 4, 8, and 12. A positive response is defined as a decrease from baseline of at least 10 points on the CAPS-5 score (Schnurr et al., 2022) and a reduction of at least 1 risk level of alcohol use, as defined by WHO (Knox et al. 2018). The treatment effect on comorbid PTSD + AUD over time will be assessed using a mixed logistic regression model. The model will be used to generate point and interval estimates of the risk differences and to test differences in proportions of PTSD+AUD resolution between treatment groups at the 8-week visit (primary timepoint), as well as at weeks 4 and 12 (secondary timepoints). The model will include fixed effects for the treatment group, visit (as a categorical variable), gender, site, presence/absence of anti-depressants, treatment-by-visit interaction, and random effects for participant (see model statement below). This approach will provide consistent estimates and valid inferences under missing at random (MAR) data assumptions while accounting for correlation among multiple measures on the same participant. This mixed model will improve the power of the study and the precision of all estimates by allowing all available measures for an individual to be incorporated in the analysis, even if other timepoints are missing. Sensitivity analysis maybe considered by excluding participants that have a low or moderate WHO risk level at baseline. This model is further described below:

$$g(E(Y_{ij})) = \beta_0 + \beta_1 \text{Visit}_{ij} + \beta_2 \text{Site}_{ij} + \beta_3 \text{Treatment}_{ij} + \beta_4 \text{Gender}_{ij} + \beta_5 \text{Anti-depressant}_{ij} + \beta_6 (\text{Treatment} * \text{Visit})_i + s_i + \varepsilon_{ij}$$

Where $g(E(\cdot))$ indicates the identity link function on the expected value of Y , Y_{ij} is the j th measure of PTSD+AUD measurement in subject i , β_0 is the intercept, β_1 through β_6 are coefficients, s_i is a random subject effect and ε_{ij} is the residual error term.

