Statistical analysis modeling will be carried out utilizing SAS/STAT PROC GLIMMIX (SAS Institute Inc. 2017) with the general structure of the SAS code for this model is listed below. Generalized linear mixed models (GLMMs) are a flexible generalization of the linear mixed effect model that allows response outcomes to have an error distribution other than the normal distribution (McCullagh, & Nelder, 1989). The GLMM will employ random intercepts for the between participants' part of the covariance model, and the within participants' part of the covariance model will be initially assumed as autoregressive. The study's primary hypothesis will be tested and associated odds ratio obtained using the 'oddsratio' statement which estimates the risk difference in PSTD+AUD resolution between the treatment arms.

```
proc glimmix data=anlydata;
  class patient treat gender visit site antidepress;
  model primoutcome = treat gender visit site antidepress
    treat*visit/ solution link=logit dist=binary oddsratio;
    random int / type=ar(1) subject=patient;
    ods select parameterestimates Oddsratios;
run;
```

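### SAP 7.1 would delete the whole site factor if the one-participant site level stops a model converging; combining that level first is a free, low-severity improvement

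*SAP*

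**What the plan says.** Four statements in the SAP bear on this.

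- **SAP 7.6** notes that "only one participant from the Wayne State site enrolled and completed the study". It also states: "Since randomization was stratified based on study site, site will be included as a term in all model-based analyses".
- **SAP 7.6** deals with the lone participant only outside the primary analysis: "this participant will be removed during sensitivity analyses so comparisons can be made between study site".
- **SAP 9.3** specifies the primary mixed logistic model: "The model will include fixed effects for the treatment group, visit (as a categorical variable), gender, site, presence/absence of anti-depressants", plus the treatment-by-visit interaction and a random participant effect. The SAS code lists site in the CLASS statement and again in "model primoutcome = treat gender visit site antidepress", with a binary distribution and logit link. Nothing merges site levels.
- **SAP 7.1** gives the fallback: "in the event a model cannot converge due to small sample sizes for a specific randomization factor, it will be removed from the model". It offers no intermediate step, such as combining a sparse level with another.

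Site is one of three stratification factors (SAP 4.3). Protocol 10.4.2 also lists site in the primary model and has no convergence rule.

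**The concern.** A fixed effect for a site with one participant is estimated from that person's records alone, at most three binary outcomes. If they are all negative or all positive, the likelihood keeps rising as the site coefficient runs to minus or plus infinity. Software may then report non-convergence, or may stop at some large, meaningless value.

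If non-convergence is reported, SAP 7.1 deletes the factor, not the sparse level. Every participant loses the site adjustment because of one person, although the two active sites have ample data to support it. Treatment is a term in the model, so convergence of the primary fit is learned only with assignments available, which SAP 4.4.2 places after database lock.

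What is at stake is whether the covariates of the single formal hypothesis test (SAP 7.7) are settled in advance. A large error in the treatment estimate is not at stake.

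**Working it through.** **1. The plan's own power figure.** SAP 6 and Protocol 10.5 use 5/45 against 17/45, two-sided alpha 0.05, and Fisher's test with the Walters approximation. With n = 45 per arm:

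power = Φ{ √(2n) × [arcsin√(p₁ − 1/(2n)) − arcsin√(p₂ + 1/(2n))] − 1.96 }

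- p₁ − 1/90 = 0.3667, arcsine 0.6504
- p₂ + 1/90 = 0.1222, arcsine 0.3571
- √90 × (0.6504 − 0.3571) = 2.782, and Φ(2.782 − 1.960) = 0.795

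This matches the 0.795 in the Protocol 10.5 table. The calculation is for an unadjusted two-by-two comparison, so it does not depend on how site is handled.

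**2. Chance that one participant's three outcomes agree.** SAP 9.3 assesses the outcome at Weeks 4, 8 and 12. Let q(u) = 1/(1 + exp(−(μ + u))), with u ~ N(0, σ²) and μ set so that the average of q equals the response rate. Then P(agree) = E[q³ + (1 − q)³]. The rates of 11% and 38% are from SAP 6. The 25% rate, the variances σ² and a constant rate across visits are assumptions, because the documents give no values for them.

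| Response rate | σ² = 1 | σ² = 4 | σ² = 9 |
|---|---|---|---|
| 11% (5/45) | 0.733 | 0.791 | 0.838 |
| 25% | 0.520 | 0.642 | 0.727 |
| 38% (17/45) | 0.413 | 0.568 | 0.672 |

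The range is 41-84%. With no participant effect (σ² = 0) it is 0.704 at 11% and 0.295 at 38%.

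**3. Does agreement cause non-convergence?** Trials of 90 people, with one person alone in a third site and negative at all three visits, were simulated and fitted with a random-intercept logistic model. SAS was not available. The software limits, random-intercept SD (1.5 in the first, second and fourth rows) and covariate mix are assumptions. The table gives the percentage of fits that met the convergence criterion.

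| Fitting method | Three-level site | Person removed | Site removed |
|---|---|---|---|
| Linearised pseudo-likelihood, 20 updates, variance estimated (200 trials) | 0% | 68.5% | 67.5% |
| Same, 100 updates and a cap on the linear predictor | 73% | 74% | 71% |
| Linearised pseudo-likelihood, 20 updates, variance fixed (200 trials) | 0% | 100% | 100% |
| Quadrature maximum likelihood, gradient criterion (150 trials) | 100% | 100% | 100% |

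Where the three-level fit stopped normally, its site coefficient was meaningless: near −24 in the second row and −12.5 in the fourth. With mixed outcomes (0, 1, 0) under the first-row settings, the three-level model met the criterion in 79% of fits. One person's pattern can therefore trigger the rule, but whether it does depends on the settings.

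**4. Effect on the treatment estimate, with that person all-negative.**

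- Removing only that person leaves the Week 8 log odds ratio essentially as in the three-level model: difference 0.000 in the pseudo-likelihood fits, median 0.0001 in the quadrature fits.
- Removing site shifts it by a median of 0.025 (95th percentile 0.10; second-row settings) or 0.04 (quadrature) with no true site effect, and by a median of 0.04 (95th percentile 0.18) with a modest one.
- exp(0.04) = 1.04, so the median shift is about 4% on the odds-ratio scale. The median standard error in the second-row fits was about 0.67.

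**5. Effect on power.** Ordinary logistic regression at 11% against 38%, 45 per arm, with and without site:

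- site odds ratio 2: 0.888 − 0.886 = 0.002
- site odds ratio 4: 0.896 − 0.892 = 0.004
- site odds ratio 8: 0.922 − 0.910 = 0.012

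The loss is 0-1 percentage point. This is not the planned mixed model and ignores the 30% attrition in SAP 6, so it indicates scale only.

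**The case against.** The strongest reply is that the trigger has not been shown to fire. SAP 7.1 acts on failure to converge, not on an infinite coefficient, and two of the four fitting set-ups stopped as often with the one-person level as without it. In the first row about a third of fits also failed with that person or site removed, so not all failures come from Wayne State. This stands. A reader might take 41-84% as the chance that site is dropped. It is only the chance that three visits agree.

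Second, a reader might infer that the primary result would be materially distorted. The calculations do not support that: the shifts are small, and keeping the degenerate level does no harm to the treatment estimate.

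Third, a reader might see SAP 7.1 and 7.6 as two incompatible primary models. A fairer reading is that 7.6 gives the default and 7.1 a prespecified exception, although neither refers to the other.

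Fourth, the SAP already recognises the one-person site and plans an analysis without that participant. This is useful mitigation, but it leaves the primary model exposed.

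Fifth, the documents do not give this participant's arm. Per SAP 1, Detroit was added in protocol version 4 and the high-dose arm was removed in version 5. If this person was in that arm, the separate SAP 7.1 rule restricting a non-converging model to low dose and placebo could take them out anyway. That possibility cannot be resolved from the text.

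None of this justifies removing a whole factor when one sparse level is the cause.

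**Conclusion.** The point holds as a low-severity weakness in the order of the fallback steps. As written, a one-person site level may stop the primary model converging, and the stated response would also discard the Tuscaloosa/West Haven adjustment on which randomization was stratified. How often this would happen in GLIMMIX is unknown. The calculations show only that it can happen, and that agreement across visits is plausible under the assumed rates and variances. The effects on power and on the treatment estimate are small. The documents do not support a claim that the primary analysis will fail or that its conclusion would change. The benefit of acting is a primary model whose site term is fixed before assignments are known.

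**What to change.** - **SAP 7.6:** state, before unmasking, that for the site covariate the Wayne State participant is combined with one named active site. Site then has two levels in the primary model and the participant remains in the intention-to-treat analysis. Keep the planned analysis without this participant as the sensitivity check.
- **SAP 7.1:** state that sparse levels of a randomization factor are combined before any factor is removed, and cross-refer to 7.6.

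The choice of active site is partly arbitrary, since either gives this person a nominal stratum. What matters is that it is named in advance. A penalised (Firth-type) fit is not needed: it would add another data-dependent switch and replace the GLIMMIX code in SAP 9.3.

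Cost: a few sentences of SAP text, with no change to data collection, sample size or participants. This is a free improvement.

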7.2 Adjustments for Covariates

Since this is a randomized, double-blind, placebo-controlled study with equal balance in the treatment arms, no adjustment for demographic or baseline characteristics is planned. However, any assessment of the impact of covariates or adjustments for them will be done in an exploratory manner only and described in the study report.

7.3 Handling of Dropouts and Missing Data

Analysis of the primary and exploratory outcomes will be based on a mixed-effect model of repeated measures (MMRM) using data from all time points to account for missing data and thereby maximize information used for the analyses. These models treat missing data as ignorable missing, assuming any missing data are missing at random. No imputation processes will be used to replace missing data. However, every effort will be made to minimize missing data.

Additionally, because missing observations have the potential to alter the results of analyses, we will examine whether the pattern of missing data is different among the groups. If there are no systematic differences between those with and without missing data, the data will be considered to be missing at random. If there are significant differences in dropout or missing data patterns between treatment arms, we will conduct sensitivity analyses to determine the impact of missing information on the treatment comparisons.

7.4 Interim Analyses and Data Monitoring

The PASA Consortium Leadership has established a Data Safety Monitoring Board (DSMB) to oversee this study. Members of the DSMB are independent of the study investigators and include representatives with substance abuse, pharmacology and psychology/psychiatry expertise, a biostatistician and an ethicist. None will have financial, scientific, or conflicts of interest which might interfere with their unbiased assessment of the progress of the trial. The DSMB will meet at least once every four months as specified in the DSMB charter to review the study, although may be convened between planned meetings to discuss study issues related to adverse events/safety. This protocol will be approved by the DSMB prior to initiation of recruitment. While there are study halting rules that will trigger a study review by the DSMB (details found in the protocol), there are no formal study stopping rules based on the safety review that would trigger permanent study termination without the review and recommendation of the DSMB.

This study may be suspended or prematurely terminated if there is reasonable cause. Written notification, documenting the reason for study suspension or termination, will be provided by the suspending or terminating party to the investigator, DoD Grants Officer Representative (GOR) for further distribution to the Programmatic Panel, PASA Consortium PI (or designee), DSMB, and regulatory authorities. If the study is prematurely terminated or suspended, the PI will promptly inform the IRB and will provide the reason(s) for the termination or suspension.

Circumstances that may warrant termination or suspension include, but are not limited to:

- A pattern of AEs indicating that SL-BUP + XR-NTX is inappropriate or unsafe
- Determination of unexpected, significant, or unacceptable risk to participants
- New information emerges that suggests the risks are increased beyond an acceptable limit and outweigh benefits
- Significant and recurring protocol violations that threaten the integrity of the study data
- Data that are not sufficiently complete and/or evaluable
- Continuing and ongoing serious noncompliance with human research protections and regulations that warrants study closure
- Determination of futility. While there are no formal assessments of futility for efficacy, the study may be terminated if operationally futile, e.g. there is an inability to enroll or retain study participants. The study may resume once concerns about safety, protocol

compliance, data quality is addressed and satisfy the PASA Consortium, IRB and/or other regulatory agencies.

- Generally, any study suspension that could occur will be based upon review of the study and recommendations made by the DSMB. Details of safety oversight and associated study halting rules are provided in Sections 8.6 and 8.5, respectively.
- A local site that is not performing for one of the reasons above, may be selectively terminated and replaced with a new site.

A description of the report to be provided to the DSMB is listed in Appendix A.

7.5 Masked Data Review

A masked data review of outcome data for this study is not planned.

7.6 Multicenter Studies

This is a 3-center study including Tuscaloosa Research & Education Advancement Corporation (TREAC)/Tuscaloosa VA Medical Center (TVAMC), Connecticut Research & Education Foundation (CREEF)/VA Connecticut Healthcare System (VACT), and Wayne State University. Although we initially expected the total number of enrolled participants to be roughly equal across the three study sites, only one participant from the Wayne State site enrolled and completed the study. Since randomization was stratified based on study site, site will be included as a term in all model-based analyses. Since only one participant was enrolled at Wayne State, this participant will be removed during sensitivity analyses so comparisons can be made between study site.

7.7 Multiple Comparisons and Multiplicity

One single primary formal hypothesis test is planned for this study at the 0.05 level of significance, which is the comparison of the SL-BUP + XR-NTX treatment group vs. placebo for the primary outcome at the primary timepoint (Week 8). Additionally, regardless of significance of the primary outcome, statistical significance of the secondary outcomes will be assessed, with adjustment for multiple comparisons using the Benjamini-Hochberg false discovery rate correction to maintain the nominal alpha level of 0.05 (Benjamini & Hochberg, 1995). Primary and secondary hypothesis tests resulting in nonsignificant p-values will be interpreted as inconclusive. All other treatment group comparisons will be considered descriptive in nature with no adjustment for multiple comparisons, and all confidence intervals will be generated using 95% bounds.

7.8 Examination of Subgroups

No subgroup analyses are planned at this time.

7.9 Assessment Windows

All screening assessments will be performed prior to Day 0 (study baseline/admission). Screening will take place over 1 to 14 days and include the study instruments listed in the table above (section 4.5). Most screening assessments are repeated at Day 0 if occurring more than one-month post screening. The most recent data collected during the screening/baseline period will be used for summarizing and analyzing baseline data.

Participants will visit their respective site to complete study procedures at weeks 1, 2, 4, 6, 8, 10, and 12. The visit windows for these in-person visits is +/- 7-days. It is important to confirm

appointment with subjects at each visit, so that if adjustments need to be made so that the subject does not run out of medication between the scheduled in-person visits. The CRC will make a telephone contact with the participant between face-to-face visits to remind the participant of the next office visit and to check on adherence to the study medication and if there have been any adverse events. While every attempt is made to retain the participant in the study on medication for the full 12 weeks, the participant may discontinue medication at any point and remain in the study for assessments through week 12. Out-of-window visits or assessments must be reported as protocol deviations. If any exclusions are made for these reasons, these exclusions will be described in the study report.

8 STUDY SUBJECT CHARACTERIZATION

8.1 Subject Disposition

Participant eligibility status will be summarized and overall disposition of study participants will be described using a standard CONSORT diagram. The number of participants randomized and those completing or discontinuing from study therapy will be summarized.

8.2 Protocol Deviations

Protocol deviations will be listed with information such as type of deviation, time of occurrence, and reason. Incidence of protocol deviations will also be summarized overall and for each protocol deviation category. Incidence rate of protocol deviations will be calculated as the number of deviations divided by number of participant days.

8.3 Study Drug Exposure and Adherence

A dosing/pill count log will record the doses given each week (or since the last in-person visits) and whether the doses were distributed and taken per protocol. A descriptive table of overall dosing will be provided along with a listing of missed doses and reasons for the missed doses. To assess medication adherence, blood samples collected at study weeks 8 and 12 will be tested for buprenorphine and its metabolite, norbuprenorphine, using quantitative assessments. Results will be summarized graphically (box-plots) over time for the active treatment study group.

8.4 Demographic and Baseline Characteristics

All data collected at baseline will be summarized descriptively for the entire efficacy (intent-to-treat) population. Demographic variables of interest include, but are not limited to, age (years), gender, race and ethnicity, veteran status, service-connected disability, and education level.

Baseline efficacy variables include, but are not limited to CAPS-5, PCL-5, %HDD, PHQ-9, and VR-12.

